10.2.2 Adverse Event Incidence

TEAE incidence will be summarized and presented using primary MedDRA system organ classes (SOCs) and preferred terms (PTs). The system organ classes will be presented in alphabetical order and the preferred terms will be presented in the alphabetical order within each system organ class. Subjects reporting more than one adverse event for a given MedDRA PT will be counted only once for that term. Subjects reporting more than one adverse event within a SOC will be counted only once for the SOC total. Subjects reporting more than one adverse event will be counted only once in the overall adverse event total.

The number and percentage of subjects experiencing one or more TEAEs will be summarized by PT for each treatment group and overall subjects. The PTs will be presented by decreasing frequency in overall subjects.

The number and percentage of subjects experiencing one or more adverse events in the following adverse event categories will be summarized by primary SOC and PT for each treatment group and overall subjects.

- Any TEAE
- Any serious TEAE
- Any TEAE that led to discontinuation of study drug
- Any TEAE assessed by the investigator to be Reasonable Possibility of Being Related to study drug

The number of subjects experiencing one or more TEAEs will also be summarized by maximum severity category (mild, moderate, severe and unknown) and primary SOC and PT for each treatment group and overall subjects. Subjects reporting more than one TEAE for a given PT will be counted only once for that term in the most severe category

reported. If a subject has an adverse event with unknown severity, then the subject will be counted in the severity category of "unknown" even if the subject has another occurrence of the same event with a severity present. The only exception is if the subject has another occurrence of the same adverse event with the most extreme severity – "Severe." In this case, the subject will be counted under the "Severe" category.

The number of subjects experiencing one or more TEAEs will also be summarized by maximum relationship category (Reasonable Possibility of Being Related, No Reasonable Possibility of Being Related and Unknown), as assessed by the investigator, and primary SOC and PT for each treatment group and overall subjects. Subjects reporting more than one TEAE for a given PT will be counted only once for that term in the most related category reported. If a subject has an adverse event with unknown relationship, then the subject will be counted in the relationship category of "unknown," even if the subject has another occurrence of the same event with a relationship present. The only exception is that if a subject has another occurrence of the same adverse event with a relationship assessment of "Reasonable Possibility of Being Related." In this case, the subject will be counted under the "Reasonable Possibility of Being Related."

10.2.3 Listing of Adverse Events

The following additional summaries of adverse events will be prepared.

- List of subject numbers associated with each PT for all TEAEs
- List of subject numbers associated with each PT for all TEAEs assessed by the investigator as Reasonable Possibility of Being Related.
- Listing of all serious adverse events
- Listing of all adverse events that led to discontinuation of study drug
- Listing of all fatal adverse events
- Listing of all deaths

10.3 Analysis of Laboratory Tests

The laboratory tests with continuous values that will be analyzed are described in [Table 1](#).

Table 1. Laboratory Tests

Hematology	Clinical Chemistry	Urinalysis
Hematocrit	Blood urea nitrogen (BUN)	Specific gravity
Hemoglobin	Creatinine	pH
Red blood cell (RBC) count	Total bilirubin	
White blood cell (WBC) count	Albumin	
Neutrophils	Aspartate aminotransferase (AST)	
Bands (if detected)	Alanine aminotransferase (ALT)	
Lymphocytes	Alkaline phosphatase	
Monocytes	Sodium	
Basophils (if detected)	Potassium	
Eosinophils (if detected)	Calcium	
Platelet count (estimate not acceptable)	Inorganic phosphate	
Mean corpuscular volume (MCV)	Uric acid	
Mean corpuscular hemoglobin concentration (MCHC)	Cholesterol	
Prothrombin time (PT)	Total protein	
Activated partial thromboplastin time (aPTT)	Glucose	
PT/INR (Prothrombin Time/International Normalized Ratio)	Triglycerides	
	Bicarbonate/Carbon Dioxide (CO ₂)	
	Chloride	

10.3.1 Potentially Clinically Significant Laboratory Values

Criteria for potentially clinically significant (PCS) values have been predefined for selected laboratory variables as outlined in [Appendix A](#). For each variable, a summary of the number and percentage of subjects in each treatment group who have at least one double-blind observation that meets the PCS criteria and is more extreme than their baseline value will be provided at any time in the entire study. A listing will also be prepared that will include, for each variable, all observations for each subject that met the PCS criteria for that variable at any time during the study.

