#### **8.1.4.3 Analysis of Laboratory Tests**

Analysis will be performed on the safety data set for laboratory tests. Change from Baseline to each visit value and to the minimum, maximum, and final value will be presented for each continuous hematology, chemistry, and urinalysis parameter. Treatment differences between treatment sequence in change from Baseline to minimum, maximum, and final clinical laboratory evaluation will be analyzed using a 1-way ANOVA with treatment sequence as the main effect.

For each treatment sequence, shift tables will be generated showing the number and percentage of subjects with low, normal, high, and missing values at Baseline and final observation based on the reference ranges provided by each laboratory. Laboratory observations will be categorized as normal, low, or high relative to the reference (normal) range associated with the laboratory that performed the assay. Details will be specified in the SAP.

The number and percentage of subjects in each treatment sequence who have values meeting predefined criteria for PCS ([Appendix D](#)) at any time after the first dose of study drug and no more than 20 weeks after the last dose of study drug will be summarized separately for hematology and chemistry variables. No comparisons between treatment sequences will be performed for PCS analysis.

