2.2.2 Visit Definitions

Definition of Rx Day (Days Relative to the First Dose of Study Drug)

Rx Day is calculated for each time point as the number of days between the day of the first dose of study drug and the specific time point. For dates before the first dose date of study drug, Rx day = date of time point – first dose date; for dates on or after the first dose date of study drug, Rx day = date of time point – first dose date + 1. Thus, Rx Day is a negative value when the time point of interest is prior to the first study drug dose day; Rx Day is a positive value when

the time point of interest is on or after the first study drug dose day. There is no Rx Day 0. With this defined algorithm, the day of the first dose of study drug will be Rx Day 1.

RxEnd Day is calculated for each post-treatment time point as the number of days between the day of the last dose of study drug and the specific time point: RxEnd Day = date of time point – last dose date. With this defined algorithm, the day of the last dose of study drug will be RxEnd Day 0.

Definition of Baseline and Final Observation

For primary efficacy analyses on the ITT data set and for safety analyses on the safety data set of the Treatment Period, "baseline" shall refer to the last non-missing observation prior to the first dose of study drug of Study M15-570.

- If the duration between Day 1 of Study M15-570 and the last dose (Week 92) of Study M15-566 is less than or equal to 45 days and no M15-570 Day 1 visit data, vital sign, laboratory, MRI, and questionnaire data at visit Week 96 of Study M15-566 will be used as the baseline for Study M15-570. If M15-570 Day 1 visit data are available, Day 1 visit data will be used as the baseline.
- If the duration between Day 1 of M15-570 and the last dose (Week 92) of Study M15-566 is larger than 45 days, Day 1 visit data of Study M15-570 of vital sign, laboratory, MRI, and questionnaire data will be the baseline. If M15-570 Day 1 visit data are not available, the last available data from M15-566 will be used as the baseline.
- Day 1 visit data of M15-570 will always be the baseline of Study M15-570 for all other data (Adverse Event, ECG) and will not be impacted by the duration between Day 1 visit of Study M15-570 and Week 92 visit of Study M15-566.

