4.2 Study Design

This Phase 2 extension of a multiple dose, multicenter, multinational, double-blind study is designed to evaluate the long-term safety and tolerability of ABBV-8E12 in subjects with early AD. The study will consist of a 5-year treatment period and a follow-up period of approximately 20 weeks following the last study drug administration.

All subjects who complete the Treatment Period in Study M15-566 will be eligible to participate in this study according to the selection criteria. Upon completion of baseline study procedures, eligible subjects will receive ABBV-8E12 via intravenous (IV) infusion on Day 1 of Study M15-570 as follows:

- Subjects who received placebo in Study M15-566 will receive 2000 mg ABBV-8E12 in Study M15-570;
- Subjects who received 300 mg ABBV-8E12 in Study M15-566 will receive 1000 mg ABBV-8E12 in Study M15-570; and
- Subjects who received 1000 mg or 2000 mg ABBV-8E12 in Study M15-566 will continue on the same dose in Study M15-570.

Note: if any changes are made to alter Study M15-566 with regards to the treatment arms due to safety, efficacy, or other reasons, a corresponding change will be implemented in Study M15-570. This change may include, but is not limited to, adding or dropping treatment arm(s).

Subjects will receive study drug infusion every 4 weeks and undergo other study procedures and assessments as outlined in the Study Activities table ([Table 2](#)). Subjects will continue to receive treatment until one of the discontinuation criteria is met, the sponsor discontinues the study, or the subject completes the 5-year treatment period of Study M15-570.

[figure not shown]
Day 1 visit of Study M15-570 (day of the first dose of Study M15-570) will be at least 4 weeks but no more than 8 weeks after the last dosing visit (Week 92) of Study M15-566. Should this window be longer than 8 weeks, the subject may be considered for participation in Study M15-570 only with the approval of the therapeutic area medical director (TA MD). The investigators and subjects will remain blinded to the treatment assignments in Study M15-566 and will be blinded to the dose level of ABBV-8E12 in Study M15-570.

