5.0 Analysis Populations and Analysis Data Set

Data Sets for Safety Analyses

Safety Data Set: The Safety Data Set will contain data from Study M15-570 only, regardless of the treatment received in Study M15-566. Baseline for the Safety Data Set will be the last observation on or before the first dose of ABBV-8E12 in Study M15-570. If no Baseline is recorded in Study M15-570, the last value in Study M15-566 will be used as the Baseline.

6.0 Demographics, Baseline Characteristics, Subject History, and Previous/Concomitant Medications

The data analysis will be conducted on Safety Data Set and among treatment groups defined as Studies M15-566/M15-570: 300/1000 mg, 1000/1000 mg, placebo/2000 mg, and 2000/2000 mg.

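### The SAP's PCS laboratory count adds an undeclared baseline filter that under-counts persistent abnormalities in sequences already on drug at the M15-570 baseline

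*SAP*

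**What the plan says.** Protocol section 8.1.4.3 plans the number and percentage of subjects in each sequence "who have values meeting predefined criteria for PCS" at any time from after the first dose to 20 weeks after the last. It sets no condition on baseline.

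SAP section 10.3.1 summarises, for each treatment group, subjects "who have at least one double-blind observation that meets the PCS criteria and is more extreme than their baseline value". Its next sentence asks for a listing of "all observations for each subject that met the PCS criteria for that variable at any time during the study", with no baseline condition.

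On baseline, SAP section 5.0 states: "Baseline for the Safety Data Set will be the last observation on or before the first dose of ABBV-8E12 in Study M15-570". It also restricts the data: "The Safety Data Set will contain data from Study M15-570 only, regardless of the treatment received in Study M15-566". Section 2.2.2 of the statistical programming plan, which is part of the SAP document, covers subjects with no Day 1 data and a gap of at most 45 days since the last M15-566 dose. For them, "vital sign, laboratory, MRI, and questionnaire data at visit Week 96 of Study M15-566 will be used as the baseline for Study M15-570".

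The columns are the sequences "300/1000 mg, 1000/1000 mg, placebo/2000 mg, and 2000/2000 mg" (SAP section 6.0). In only one of them was the subject off drug before baseline: "Subjects who received placebo in Study M15-566 will receive 2000 mg ABBV-8E12 in Study M15-570" (SAP section 4.2).

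SAP section 13.0 reports that the efficacy, PK and biomarker sections and some safety analyses were removed. It does not mention a narrower PCS definition.

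**The concern.** Requiring a value to be worse than baseline is a reasonable way to set aside abnormalities that were there before treatment, provided baseline is drug-free. Here that is true only of placebo/2000 mg. In 1000/1000 mg and 2000/2000 mg, and to a lesser degree 300/1000 mg, baseline comes after the whole M15-566 treatment period. An abnormality that arose on drug in M15-566 and persists then becomes the reference value. It stays out of the count unless it worsens.

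The primary objective is long-term safety and tolerability. The list of tables in the programming plan has no laboratory shift table and no change-from-baseline table, although protocol section 8.1.4.3 planned both. The PCS counts are thus the only laboratory summary percentages left, and no other laboratory summary table would show a persistent shift.

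**Working it through.** The plan gives no figure for this rule, so there is none to reproduce. The check has four steps.

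**1. Is baseline on drug?** Protocol section 5.1 places Day 1 about 4 and no more than 8 weeks after the Week 92 visit of M15-566, the last dosing visit. Protocol section 6.1.4 equates 20 weeks with about 5 half-lives, so one half-life is 20/5 = 4 weeks. The exposure left from the last dose is 2^(-weeks/4):
- 4 weeks: 2^(-1) = 50%
- 8 weeks: 2^(-2) = 25%

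Baseline is on drug in the three sequences that received active treatment in M15-566.

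**2. Whom can the filter remove?** A value beyond a PCS limit is ordinarily more extreme than any baseline inside that limit. In practice the filter bites only on subjects who are already PCS at the M15-570 baseline.

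**3. What share of stable cases is lost?** Take a subject whose abnormality is stable and always beyond the limit. The baseline and k later values are then exchangeable, and the subject is missed when baseline is the most extreme of the k+1 values. The probability is 1/(k+1). The programming plan schedules laboratory tests at Weeks 12, 24, 48, 72, 96, 144, 192, 240 and 260, so k is at most 9 on treatment.

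| k | Missed, 1/(k+1) | Counted of 5 affected per 100 (assumed), continued dose | Same, placebo/2000 mg |
|---|---|---|---|
| 1 | 50% | 2.5 | 5 |
| 2 | 33% | 3.3 | 5 |
| 3 | 25% | 3.75 | 5 |
| 9 | 10% | 4.5 | 5 |

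The protocol's rule counts all 5 in every sequence. A simulation with a milder abnormality (mean 3.5 × ULN, PCS limit 3 × ULN, within-subject CV 40%; all but the limit assumed) gave the following shares counted:
- SAP rule, on-drug baseline: 44% (k=1), 74% (k=3), 90% (k=9)
- Protocol rule, and SAP rule in placebo/2000 mg: 66%, 96%, 100%

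**4. How large is the gap across all subjects?** This depends on the drug shift, which the documents do not give. Assumed model: unit variance, 70% of it between subjects, PCS limit at 2.5 SD, the same shift in every subject while on drug, k=2, and 2,000,000 simulated subjects.

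| Shift | Already PCS at on-drug baseline | Counted, drug-free baseline | Counted, on-drug baseline | Gap (points) |
|---|---|---|---|---|
| 0.5 SD | 2.3% | 3.7% | 3.3% | 0.4 |
| 1 SD | 6.7% | 10.5% | 8.9% | 1.6 |
| 2 SD | 30.9% | 41.9% | 32.2% | about 10 |

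The unfiltered counts were 3.8%, 10.5% and 41.9%. The filter costs a drug-free baseline almost nothing, so the gap comes from the on-drug baseline.

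**The case against.** **Nothing is hidden from the report.** A reader might infer that persistent abnormalities vanish. They do not. The PCS listing, programmed as Tables 14.3__3.2 and 14.3__4.2, has no filter, and Appendices 16.2__7.1 to 16.2__7.3 list the laboratory determinations themselves. Only the summary count is narrowed. This stands, although a listing gives no percentages.

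**The affected group may be small.** Only subjects already PCS at the M15-570 baseline are exposed to the filter. Exclusion criterion 1 asks the investigator to re-evaluate anyone with an interim significant hematological, hepatic, renal or metabolic disorder, and entrants must have completed M15-566. Protocol section 3.2 reports no clinically relevant pattern of abnormal laboratory findings. A 2-SD shift, which would make about 31% of subjects PCS at baseline, is therefore an extreme assumption. This stands, and it is why the size has to be shown as a range.

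**The three sequences are not alike.** It is tempting to treat every sequence with prior active treatment as equally affected. In 300/1000 mg the dose rises at Day 1, so a dose-related worsening would tend to exceed baseline and be counted. The full effect is confined to 1000/1000 mg and 2000/2000 mg.

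**There is no biased treatment comparison.** A reader might infer that a test between sequences is distorted. SAP section 10.1 plans no comparisons between treatment groups unless otherwise specified, and protocol section 8.1.4.3 rules them out for PCS. The harm is to descriptive reading of percentages set side by side.

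**The data set is M15-570 only by design.** One may argue that toxicity arising in M15-566 belongs to that study. That explains the choice of baseline. It does not explain why an abnormality still present during M15-570 treatment should be left out of a count that the protocol defines without reference to baseline.

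**Conclusion.** The point holds for the summary count. SAP section 10.3.1 narrows the protocol's PCS definition, section 13.0 does not say so, and the narrowing acts differently by sequence. It under-reports persistent abnormalities already PCS at an on-drug baseline, mainly in 1000/1000 mg and 2000/2000 mg and less in 300/1000 mg. Relative to the protocol rule, the filter can only lower a count.

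For a stable abnormality always beyond the limit, the loss is between 10% (all nine visits) and 50% (one later sample) of affected subjects. Early termination moves subjects towards the higher figure, but the documents do not say how far. The effect on the tabulated percentages could be a fraction of a point or, under a large shift, about 10 points. The number of later samples, the shift, the within-subject variability and the PCS rate at baseline are all assumptions here. The documents do not support a claim that a drug-related abnormality exists, or that the filter was chosen to conceal one. This is a cheap improvement to reporting and does not threaten the study's conclusions.

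**What to change.** In Tables 14.3__3.1 and 14.3__4.1, report the protocol count for each sequence: any PCS value after the first dose and up to 20 weeks after the last, with no baseline condition. Keep the filtered count beside it, labelled as PCS and more extreme than the M15-570 baseline. Amend SAP section 10.3.1 to define both, and name the added filter in SAP section 13.0 as a change from protocol section 8.1.4.3.

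The cost is one extra column per table. The protocol column will show slightly higher PCS counts, because it includes abnormalities that predate M15-570, whether drug-related or not. The difference between the two columns shows the reader how many such subjects each sequence has.

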10.4 Analysis for Other Safety Variables

10.4.1 Columbia-Suicide Severity Rating Scale (C-SSRS)

Number and percentage of subjects in the following categories will be summarized for each treatment group and overall subjects by visit and for the entire study:

- Answered 'Yes' to each C-SSRS item
- Had suicidal ideation (defined as answering 'Yes' to one or more suicidal ideation items)
- Had suicidal ideation only (defined as answering 'Yes' to one or more suicidal ideation items and answering 'No' to all suicidal behavior items)
- Had suicidal behavior (defined as answering 'Yes' to one or more suicidal behavior items)
- Had suicidal ideation or behavior (defined as answering 'Yes' to one or more suicidal ideation or behavior items)

10.4.2 Summary of MRI Safety Evaluations

MRI safety evaluations will be summarized by treatment sequences placebo/2000mg, 2000/2000mg, 300/1000mg, and 1000/1000mg based on MRI evaluations in the double blinded period. The summaries include number and percentage of subjects with presence and severity of baseline and post baseline MRI findings of cerebral edema, microhemorrhages, and severe white matter disease as defined by a score of 3 on Age-Related White Matter Changes (ARWMC) scale and other structural abnormalities. Descriptive statistics (mean, median, minimum, maximum) of number of new microhemorrhages or new lesions in the double-blinded period will be presented. Listing of subjects with post-baseline MRI findings will be provided.

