#### **Magnetic Resonance Imaging**

For all subjects, a MRI will be obtained at time points indicated in the Study Activities table ([Appendix C](#)) and interpreted by a radiologist or neurologist. Subjects will be queried to assure they do not have specific contraindications for MRI.

MRI assessment at Day 1 will be used as baseline for evaluating changes during the study. Signal abnormalities on FLAIR or T2 weighted images will be evaluated to determine the presence of infectious, vascular, neoplastic, or other degenerative processes. The 3D T1 weighted sequences will also be acquired for volumetric analysis that will enable a quantitative assessment of the whole and regional brain volume.

On-treatment safety MRI analysis will be performed at the time points indicated in the Study Activities table. On-treatment volumetric MRI analysis will be performed at the time points indicated in the Study Activities table starting from Baseline.

The MRI scan should be done prior to the optional LP, if applicable. Otherwise at least a 3-day window between the LP and the MRI appointment is necessary. Details of the MRI procedures will be described in the MRI Procedures Manual provided by the sponsor.

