## **5.4 Removal of Subjects from Therapy or Assessment**

### **5.4.1 Discontinuation of Individual Subjects**

Each subject has the right to withdraw from the study at any time. In addition, the investigator may discontinue a subject from the study at any time if the investigator considers it necessary for any reason, including the occurrence of an AE or noncompliance with the protocol.

The subject will be discontinued from the study if any of the following occur:

- Subject starts receiving an approved disease-modifying therapy for AD or a biologic medication for the treatment of AD.
- Subject develops unacceptable toxicity.
- Female subject becomes pregnant.
- Investigator decides it is in the subject's best interest to discontinue.
- Subject is noncompliant with the protocol based on the investigator or medical monitor assessment.
- Subject withdraws consent.
- Subject is lost to follow-up despite reasonable efforts by the investigator to locate the subject.

Subjects with the following AEs will be considered for treatment discontinuation:

- Severe or life-threatening allergic reactions will require the immediate interruption of ABBV-8E12 treatment, permanent discontinuation from further treatment and initiation of appropriate medical therapy and follow-up.
- Life-threatening drug related AEs of nervous system will require discontinuation from further treatment with ABBV-8E12, initiation of appropriate medical therapy and follow-up.

All moderate and severe symptomatic neurological abnormalities and treatment-emergent MRI findings will be reported to AbbVie TA MD and subjects will be considered for discontinuation from treatment and may be permitted to continue in the study only after a management plan is discussed with the AbbVie TA MD.

Subjects with unexpected worsening of cognitive impairment or dementia will be reported to AbbVie TA MD and considered for discontinuation from treatment and may be permitted to continue in the study only after a management plan is discussed with the AbbVie TA MD.

Subjects at risk of suicide as indicated by answering yes to question 4 or 5 on the C-SSRS and determined by the investigator to be at risk of suicide should be discontinued from participation in the study and referred for appropriate follow-up care.

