TABLE 14.3__1.4	SUBJECTS WITH TREATMENT-EMERGENT ADVERSE EVENTS BY SYSTEM ORGAN CLASS, PREFERRED TERM AND MAXIMUM RELATIONSHIP TO STUDY DRUG (SAFETY DATA SET)
TABLE 14.3__1.5	SUBJECTS WITH TREATMENT-EMERGENT ADVERSE EVENTS BY SYSTEM ORGAN CLASS, PREFERRED TERM AND MAXIMUM SEVERITY (SAFETY DATA SET)
TABLE 14.3__1.6	NUMBER AND PERCENTAGE OF SUBJECTS WITH TREATMENT-EMERGENT ADVERSE EVENTS BY PREFERRED TERM IN DESCENDING ORDER OF INCIDENCE (SAFETY DATA SET)
TABLE 14.3__1.7.1	LISTING OF SUBJECT NUMBERS ASSOCIATED WITH EACH PT FOR ALL TREATMENT-EMERGENT ADVERSE EVENTS (SAFETY DATA SET)
TABLE 14.3__1.7.2	LISTING OF SUBJECT NUMBERS ASSOCIATED WITH EACH PT FOR ALL TREATMENT-EMERGENT ADVERSE EVENTS ASSESSED BY THE INVESTIGATOR AS HAVING REASONABLE POSSIBILITY OF BEING RELATED (SAFETY DATA SET)
TABLE 14.3__2.1.1	NUMBER AND PERCENTAGE OF SUBJECTS WITH SERIOUS TREATMENT-EMERGENT ADVERSE EVENTS BY SYSTEM ORGAN CLASS AND PREFERRED TERM (SAFETY DATA SET)
TABLE 14.3__2.1.2	LISTING OF SERIOUS ADVERSE EVENTS (SAFETY DATA SET)
TABLE 14.3__2.2.1	NUMBER AND PERCENTAGE OF SUBJECTS WITH TREATMENT-EMERGENT ADVERSE EVENTS LED TO DISCONTINUATION OF STUDY DRUG BY SYSTEM ORGAN CLASS AND PREFERRED TERM (SAFETY DATA SET)
TABLE 14.3__2.2.2	LISTING OF ADVERSE EVENTS THAT LED TO DISCONTINUATION OF STUDY DRUG (SAFETY DATA SET)
TABLE 14.3__2.3.1	NUMBER AND PERCENTAGE OF SUBJECTS WITH FATAL ADVERSE EVENTS INCLUDING EATHS BY SYSTEM ORGAN CLASS AND PREFERRED TERM (SAFETY DATA SET)
TABLE 14.3__2.3.2	LISTING OF FATAL ADVERSE EVENTS (SAFETY DATA SET)
TABLE 14.3__2.4	LISTING OF SUBJECT DEATHS (SAFETY DATA SET)
TABLE 14.3__3.1	NUMBER AND PERCENTAGE OF SUBJECTS MEETING CRITERIA FOR POTENTIALLY CLINICALLY SIGNIFICANT HEMATOLOGY (SAFETY DATA SET)
TABLE 14.3__3.2	LISTING OF SUBJECTS MEETING CRITERIA FOR POTENTIALLY CLINICALLY SIGNIFICANT HEMATOLOGY (SAFETY DATA SET)
TABLE 14.3__4.1	NUMBER AND PERCENTAGE OF SUBJECTS MEETING CRITERIA FOR POTENTIALLY CLINICALLY SIGNIFICANT CHEMISTRY (SAFETY DATA SET)

TABLE 14.3__4.2	LISTING OF SUBJECTS MEETING CRITERIA FOR POTENTIALLY CLINICALLY SIGNIFICANT CHEMISTRY (SAFETY DATA SET)
TABLE 14.3__5	SUMMARY OF C-SSRS (SAFETY DATA SET)
TABLE 14.3__6.1	SUMMARY OF NUMBER AND PERCENTAGE OF SUBJECTS PERTAINING CEREBRAL EDEMA, MICRO- AND MACRO-HAEMORRHAGES, WHITE MATTER HYPERINTENSITIES (SAFETY DATA SET)
TABLE 14.3__6.2	NUMBER AND PERCENTAGE OF SUBJECTS WITH PRESENCE AND INCREASING SEVERITY OF CEREBRAL OEDEMA (SAFETY DATA SET)

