TABLE 14.3__6.3	NUMBER AND PERCENTAGE OF SUBJECTS WITH NEW MICRO-HEMORRHAGES SINCE THE LAST VISIT (SAFETY DATA SET)
TABLE 14.3__6.4	NUMBER AND PERCENTAGE OF SUBJECTS WITH WHITE MATTER HYPERINTENSITIES CHANGE (ARWMC SCORE) SINCE THE LAST VISIT (SAFETY DATA SET)
TABLE 14.3__6.5	DESCRIPTIVE STATISTICS OF NUMBER OF NEW MICRO-HEMORRHAGES AND CHANGES OF ARWMC SCORES OVER TIME (SAFETY DATA SET)
TABLE 14.3__6.6	LISTING OF SUBJECTS WITH POST-BASELINE MRI FINDINGS (SAFETY DATA SET)
APPENDIX 16.2__1	STUDY AND STUDY DRUG COMPLETION
APPENDIX 16.2__2.1	INCLUSION/EXCLUSION CRITERIA
APPENDIX 16.2__2.2	PROTOCOL DEVIATIONS
APPENDIX 16.2__2.3	PREGNANCY TEST
APPENDIX 16.2__3	SUBJECTS EXCLUDED FROM THE EFFICACY ANALYSIS
APPENDIX 16.2__4.1	SUBJECT DEMOGRAPHICS
APPENDIX 16.2__4.2	SUBJECT MEDICAL/SURGICAL HISTORY
APPENDIX 16.2__4.3	TOBACCO AND ALCOHOL USE
APPENDIX 16.2__4.4	NEUROLOGICAL EXAMINATION
APPENDIX 16.2__4.5.1	COLUMBIA-SUICIDE SEVERITY RATING SCALE (C-SSRS - BASELINE) SCORE
APPENDIX 16.2__4.5.2	COLUMBIA-SUICIDE SEVERITY RATING SCALE (C-SSRS - SINCE LAST VISIT) SCORE
APPENDIX 16.2__4.6	ALZHEIMER'S DISEASE HISTORY
APPENDIX 16.2__5	STUDY DRUG ADMINISTRATION
APPENDIX 16.2__6.1	ADVERSE EVENTS

APPENDIX 16.2__6.2	SUBJECT DEATHS
APPENDIX 16.2__6.3	CONCOMITANT NON-AD MEDICATIONS AND SUPPLEMENTS
APPENDIX 16.2__6.4	SERIOUS ADVERSE EVENTS RELEVANT MICROBIOLOGY DATA
APPENDIX 16.2__6.5	SERIOUS ADVERSE EVENTS RELEVANT LABORATORY DATA
APPENDIX 16.2__6.6	SERIOUS ADVERSE EVENTS ADDITIONAL NON-PROTOCOL DIAGNOSTIC/THERAPEUTIC PROCEDURES
APPENDIX 16.2__7.1.1	HEMATOLOGY DETERMINATIONS - PART 1
APPENDIX 16.2__7.1.2	HEMATOLOGY DETERMINATIONS - PART 2
APPENDIX 16.2__7.1.3	HEMATOLOGY DETERMINATIONS - PART 3
APPENDIX 16.2__7.1.4	HEMATOLOGY DETERMINATIONS - COMMENTS AND VALUES OUTSIDE THE REFERENCE RANGE
APPENDIX 16.2__7.2.1	CHEMISTRY DETERMINATIONS - PART 1
APPENDIX 16.2__7.2.2	CHEMISTRY DETERMINATIONS - PART 2
APPENDIX 16.2__7.2.3	CHEMISTRY DETERMINATIONS - PART 3
APPENDIX 16.2__7.2.4	CHEMISTRY DETERMINATIONS - PART 4
APPENDIX 16.2__7.2.5	CHEMISTRY DETERMINATIONS - PART 5
APPENDIX 16.2__7.2.6	CHEMISTRY DETERMINATIONS - COMMENTS AND VALUES OUTSIDE THE REFERENCE RANGE
APPENDIX 16.2__7.3.1	URINALYSIS DETERMINATIONS - PART 1
APPENDIX 16.2__7.3.2	URINALYSIS DETERMINATIONS - PART 2
APPENDIX 16.2__7.3.3	URINALYSIS DETERMINATIONS - PART 3
APPENDIX 16.2__7.3.4	URINALYSIS DETERMINATIONS - COMMENTS AND VALUES OUTSIDE THE REFERENCE RANGE
APPENDIX 16.2__7.4	VITAL SIGNS

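### SAP 10.4.2 and the SPP tables count different subjects for white matter and micro-hemorrhage on MRI, and neither ties n (%) with new or worsened findings to the M15-570 baseline

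*SAP*

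**What the plan says.** SAP 10.4.2 summarises MRI safety by the four treatment sequences. It asks for the "number and percentage of subjects with presence and severity of baseline and post baseline MRI findings of cerebral edema, microhemorrhages", and for "severe white matter disease as defined by a score of 3 on Age-Related White Matter Changes (ARWMC) scale and other structural abnormalities". It adds mean, median, minimum and maximum for the "number of new microhemorrhages or new lesions in the double-blinded period will be presented", and a listing of subjects with post-baseline findings.

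The SPP, which states that it elaborates SAP version 2.0, lists six MRI outputs in its section 4.0 Appendix:

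- Table 14.3__6.1: an overview of subjects with "CEREBRAL EDEMA, MICRO- AND MACRO-HAEMORRHAGES, WHITE MATTER HYPERINTENSITIES", with no threshold or reference scan.
- Table 14.3__6.2: subjects with presence and increasing severity of cerebral edema, with no reference scan named.
- Table 14.3__6.3: "NUMBER AND PERCENTAGE OF SUBJECTS WITH NEW MICRO-HEMORRHAGES SINCE THE LAST VISIT".
- Table 14.3__6.4: "NUMBER AND PERCENTAGE OF SUBJECTS WITH WHITE MATTER HYPERINTENSITIES CHANGE (ARWMC SCORE) SINCE THE LAST VISIT".
- Table 14.3__6.5: descriptive statistics on the number of new micro-hemorrhages and on ARWMC change over time.
- Table 14.3__6.6: the listing of post-baseline findings.

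SPP section 2.2.2 defines the safety baseline relative to the first M15-570 dose and names MRI in its rules. The protocol's Magnetic Resonance Imaging text makes the Day 1 scan the baseline for changes during the study and has signal abnormalities read "to determine the presence of infectious, vascular, neoplastic, or other degenerative processes". Protocol 5.4.1 says that "treatment-emergent MRI findings will be reported to AbbVie TA MD".

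**The concern.** Long-term safety is the primary objective. SAP version 2.0 removed the efficacy, PK and biomarker analyses and some safety analyses. Its section 10 keeps adverse events, potentially clinically significant laboratory values, C-SSRS and MRI. The SAP and SPP should therefore describe the same MRI outcomes.

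A count of presence after baseline includes lesions that were there before the first M15-570 dose. A count of change since the last visit has a reference that moves with every scan, so slow accrual can be spread over several visits. Neither is a count of subjects who became worse than they were at entry to this study. The same SAP applies that logic elsewhere: a treatment-emergent adverse event must begin or worsen on or after the first dose (10.2), and a laboratory value must be more extreme than the subject's baseline to count (10.3.1). Section 10.4.2 states no such rule.

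**Working it through.** The documents give no rate, precision or sample size for MRI findings, so there is no figure of the plan to reproduce. The check compares the texts and then enumerates which score patterns each rule flags.

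**Step 1. The outputs side by side.**

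| Finding | SAP 10.4.2 | SPP table list | Result |
|---|---|---|---|
| White matter | subjects with ARWMC score of 3, baseline and post-baseline | hyperintensities without threshold (6.1); ARWMC change since last visit (6.4) | differ |
| Micro-hemorrhage, subjects | presence and severity, baseline and post-baseline | named without reference (6.1); new since last visit (6.3) | differ |
| Micro-hemorrhage, number of new lesions | descriptive statistics | descriptive statistics (6.5) | agree |
| Cerebral edema | presence and severity | presence and increasing severity (6.2) | presence agrees; worsening only in SPP, reference scan not named |
| Macro-haemorrhage | not named | named (6.1) | possible mismatch |
| Other structural abnormalities | named | in no count title; findings listing (6.6) | possible mismatch |

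**Step 2. ARWMC.** Assumption: an ordinal score of 0 to 3 (the SAP names only the score of 3). SAP rule: any post-baseline score of 3. SPP rule: any rise since the previous scan. The SPP title says only change, and counting falls as well would widen the gap.

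- One later scan, 4 × 4 = 16 patterns. The SAP rule flags 4 (0, 1, 2 or 3 moving to 3). The SPP rule flags 6 (0 to 1, 0 to 2, 0 to 3, 1 to 2, 1 to 3, 2 to 3). Both flag 3. SAP only: 4 − 3 = 1 (3 staying at 3). SPP only: 6 − 3 = 3 (0 to 1, 0 to 2, 1 to 2).
- Two later scans, 4 × 4 × 4 = 64 patterns. Both flag 24, SAP only 4, SPP only 20.
- Compared with baseline, over two later scans: of the 24 + 4 = 28 patterns the SAP rule flags, 7 never exceed the baseline score. Of the 24 + 20 = 44 the SPP rule flags, 10 never exceed it (for example 2, 1, 2). Neither rule equals worse than baseline.

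**Step 3. Micro-hemorrhage.** Take 0, 1 or 2 lesions at baseline and 0, 1 or 2 new ones at each of two scans: 3 × 3 × 3 = 27 patterns, with lesions persisting once seen. Presence and new since the last visit disagree in 2, the subjects with baseline lesions and none new. New since the last visit, pooled over both scans, and new since baseline disagree in 0, provided baseline is the first reference scan and none is missing. Table 14.3__6.3 would thus give the baseline count if pooled, but its title does not say that it is.

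**Step 4. Purely illustrative.** If a share p of subjects had a new lesion at each of the four non-optional scans to Week 96 (Weeks 12, 24, 48, 96), independently, a by-visit table shows p each time, while the share with any new lesion is 1 − (1 − p)^4. For p = 2%, 4% and 6% that is 7.8%, 15.1% and 21.9%. These rates are assumed.

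**Step 5. The reference scan.** Protocol Appendix C makes MRI optional at Weeks 72, 120, 168 and 216, and scans missed because of COVID-19 move to the next onsite visit. The interval behind the last visit therefore differs between subjects.

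**The case against.** The SPP gives table titles only, with no shells or footnotes. Table 14.3__6.1 could carry a score-of-3 row, and presence tables and change tables can both be programmed. A reader might infer that the programmer must choose one text over the other; the documents do not show that.

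A reader might also infer that neither text counts new or worsened findings at all. That is wrong. Both plan statistics on the number of new micro-hemorrhages, Table 14.3__6.2 counts increasing edema severity, and Table 14.3__6.3 counts subjects with new micro-hemorrhages.

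The SAP's list of summaries is not worded as exhaustive, and its other structural abnormalities could cover macro-haemorrhage. Other findings appear in the listing and in Appendix 16.2__7.6.1, and would enter the adverse event tables if reported as adverse events. Nor does protocol 5.4.1 settle the analysis: it is a reporting and discontinuation rule and does not define a treatment-emergent MRI finding. Finally, the output is descriptive, for an abbreviated report with no planned comparisons between groups, and the listing helps re-tabulation.

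Most of this stands, and it reduces macro-haemorrhage and other structural abnormalities to possible mismatches. It does not remove the two clear differences. No SPP title carries the score of 3, SAP 10.4.2 does not mention ARWMC change, and the since-last-visit reference is in the SPP titles themselves. Showing baseline and post-baseline presence separately does not help either: without cross-classification, the two percentages do not say how many subjects are new cases.

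**Conclusion.** The point holds in a limited form. The subject-level counts for white matter and for micro-hemorrhage differ between the two texts, so different subjects can count. Neither text makes the M15-570 baseline the reference for n (%) of subjects with new or worsened findings, although SPP 2.2.2 already defines that baseline for MRI.

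Its size can be stated only as patterns. With one later scan, the rules disagree on 1 + 3 = 4 of 16 ARWMC patterns, assuming a 0 to 3 score and counting rises only. A reader might infer that by-visit tables understate micro-hemorrhage several-fold in this trial. The documents do not support that: the contrast in Step 4 follows from assumed rates, four complete scans and a purely by-visit display, and it disappears if Table 14.3__6.3 is pooled over complete scans. This is an inexpensive correction to a descriptive safety summary, and no collected data are compromised.

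**What to change.** In SAP 10.4.2 and SPP Table 14.3__6.1, add for each sequence and overall the n (%) of subjects with at least one post-baseline scan showing, relative to the M15-570 baseline of SPP 2.2.2:

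- new or worsened cerebral edema;
- any new micro-hemorrhage, cumulative over scans;
- any increase in ARWMC score and, on a separate row, a score of 3 not present at baseline.

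Name macro-haemorrhage and new other structural abnormalities in both texts. State the baseline in the MRI section itself, because SAP 4.6.1 uses the M15-566 baseline for volumetric MRI. Keep Tables 14.3__6.3 and 14.3__6.4 as supporting by-visit displays.

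The cost is a few sentences and some re-specified rows, with no new scans or data. The one small drawback is that cumulative percentages will look higher than per-visit ones, which a footnote can explain.
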